### 8.4.2 Analysis of Secondary Endpoints

For analysis of secondary endpoints, progression-free survival at 6 months is defined as the proportion of subjects alive and progression-free 6 months (182 days) after study day 1. Duration of PFS is defined as the time from the study day 1 to the earlier of disease progression or death due to any cause. The analysis of PFS will include only objective progression events per RECIST and clinical progression determined by the investigator may not be considered disease progression. Subjects who do not have any post-baseline tumor assessments will be right-censored on the date of study day 1. Subjects who receive subsequent anti-cancer therapy before experiencing an event will be right censored at the date of the last tumor assessment prior to the date of initiation of subsequent therapy. Subjects who have not experienced an event (and are not otherwise censored) at the time of data cutoff will be right censored on the date of their last tumor assessment. PFS will be estimated as a sample proportion based upon the results of 6-month tumor assessment. Subjects for whom the assessment is not performed will be included as failure, even if known to be alive at this timepoint. 95% confidence intervals will be provided. Median of PFS and duration of PFS will also be estimated using Kaplan-Meier methods with associated confidence intervals.

For analysis of overall survival, duration of OS is defined as the time from study day 1 to death due to any cause. For subjects who are alive at the time of data cutoff or are permanently lost to follow-up, duration of OS will be right censored at the date the subject was last known to be alive. The median duration of OS will be estimated using the Kaplan-Meier methods with the associated confidence intervals.

### 8.4.3 Other Analyses

## 8.5 Evaluation of Safety

Each verbatim adverse event (AE) term recorded during the study will be mapped to a system organ class and preferred term using the MedDRA Dictionary, version 16.1. The duration of an

adverse event will be computed as the stop date/time minus the start date/time, expressed as days.

A treatment-emergent adverse event (TEAE) will be defined as one with a start date and time which occurred after the date and time of the first study drug administration. If the start date and time of an AE is incomplete or missing, the event will be assumed to be treatment emergent, unless the incomplete start date and time or the stop date (complete or incomplete) clearly indicates that the event started prior to the first dose of study drug. Incomplete/missing information will be reported as incomplete/missing in the subject data listings.

The relationship of each AE to study drug will be recorded as "not related," "probably not related," "possibly related," "probably related" and "definitely related." For all analysis "possibly related," "probably related" and "definitely related" will be considered as related to study drug. If a relation is missing for a given event, the event will conservatively be assumed as "definitely related" for summarization.

The severity of each AE will be classified as mild, moderate, severe, or potentially life threatening. All summaries of AEs will present the number and percentage of subjects who experienced at least one event overall, by system organ class, and by preferred term. If a subject had multiple occurrences of a particular event, the subject was counted only once at the given level of summarization (overall, within system organ class, or within preferred term).

For summaries of adverse events by maximum severity or maximum relation to study drug, if a subject had multiple occurrences of a particular AE, the subject was counted only once at the maximum severity or relation to study drug at the given level of summarization (overall, within system organ class, or within preferred term).

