#### **6.2 Clinical Procedures/Assessments**

##### **6.2.1 Adverse Event (AE) Monitoring**

The investigator or qualified designee will assess each subject to evaluate for potential new or worsening AEs as specified in the Trial Flow Chart and more frequently if clinically indicated. Adverse experiences will be graded and recorded throughout the study and during the follow-up period according to NCI CTCAE Version 4.0. Toxicities will be characterized in terms regarding seriousness, causality, toxicity grading, and action taken with regard to trial treatment.

For subjects receiving treatment all AEs of unknown etiology associated with treatment exposure should be evaluated to determine if it is possibly an event of clinical interest (ECI) of a potentially immunologic etiology (termed immune-related adverse events, or irAEs).

Please refer to Section 7 for detailed information regarding the assessment and recording of AEs.

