## **7 Assessing and Recording Adverse Events**

An adverse event is defined as any untoward medical occurrence in a patient or clinical investigation subject administered a pharmaceutical product and which does not necessarily have to have a causal relationship with this treatment. An adverse event can therefore be any unfavorable and unintended sign (including an abnormal laboratory finding, for example),

symptom, or disease temporally associated with the use of a medicinal product or protocol-specified procedure, whether or not considered related to the medicinal product or protocol-specified procedure. Any worsening (i.e., any clinically significant adverse change in frequency and/or intensity) of a preexisting condition that is temporally associated with the use of the Merck's product, is also an adverse event.

Changes resulting from normal growth and development that do not vary significantly in frequency or severity from expected levels are not to be considered adverse events. Examples of this may include, but are not limited to, teething, typical crying in infants and children and onset of menses or menopause occurring at a physiologically appropriate time.

Merck product includes any pharmaceutical product, biological product, device, diagnostic agent or protocol-specified procedure, whether investigational (including placebo or active comparator medication) or marketed, manufactured by, licensed by, provided by or distributed by Merck for human use.

Adverse events may occur during the course of the use of Merck product in clinical trials, or as prescribed in clinical practice, from overdose (whether accidental or intentional), from abuse and from withdrawal.

Progression of the cancer under study is not considered an adverse event.

All adverse events that occur after the consent form is signed but before treatment allocation/randomization must be reported by the investigator if they cause the subject to be excluded from the trial, or are the result of a protocol-specified intervention, including but not limited to washout or discontinuation of usual therapy, diet, placebo treatment or a procedure.

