#### **7.4 Evaluating Adverse Events**

An investigator who is a qualified physician will evaluate all adverse events according to the NCI Common Terminology for Adverse Events (CTCAE), version 4.0. Any adverse event which changes CTCAE grade over the course of a given episode will have each change of grade recorded on the adverse event case report forms/worksheets.

All adverse events regardless of CTCAE grade must also be evaluated for seriousness.

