	Is an overdose (whether accidental or intentional). Any adverse event associated with an overdose is considered a serious adverse event for collection purposes. An overdose that is not associated with an adverse event is considered a non-serious event of clinical interest and must be reported within 24 hours to the Sponsor and to Merck within 2 working days..	
	Other important medical events that may not result in death, not be life threatening, or not require hospitalization may be considered a serious adverse event when, based upon appropriate medical judgment, the event may jeopardize the subject and may require medical or surgical intervention to prevent one of the outcomes listed previously (designated above by a †).	
Duration	Record the start and stop dates of the adverse event. If less than 1 day, indicate the appropriate length of time and units	
Action taken	Did the adverse event cause Merck product to be discontinued?	
Relationship to Merck Product	Did Merck product cause the adverse event? The determination of the likelihood that Merck product caused the adverse event will be provided by an investigator who is a qualified physician. The investigator's signed/dated initials on the source document or worksheet that supports the causality noted on the AE form, ensures that a medically qualified assessment of	

	
causality was done. This initialed document must be retained for the required regulatory time frame. The criteria below are intended as reference guidelines to assist the investigator in assessing the likelihood of a relationship between the test drug and the adverse event based upon the available information.
 
The following components are to be used to assess the relationship between Merck product and the AE; the greater the correlation with the components and their respective elements (in number and/or intensity), the more likely Merck product caused the adverse event (AE):

	
Exposure      Is there evidence that the subject was actually exposed to Merck product such as: reliable history, acceptable compliance assessment (pill count, diary, etc.), expected pharmacologic effect, or measurement of drug/metabolite in bodily specimen?

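### Section 8.5 defines treatment emergence by start date alone, so an adverse event on record before the first dose that later rises in grade is not treatment-emergent

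*Combined protocol and SAP*

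**What the plan says.** Section 8.5 (Evaluation of Safety) gives the definition, with initial dosing as the reference point: "A treatment-emergent adverse event (TEAE) will be defined as one with a start date and time which occurred after the date and time". For incomplete or missing dates, "the event will be assumed to be treatment emergent, unless the incomplete start date and time or the stop date" makes clear that it began before dosing. Neither sentence mentions a change in grade.

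The same section then describes the tables: "All summaries of AEs will present the number and percentage of subjects who experienced at least one event overall", and by system organ class and preferred term. It does not say whether these tables are limited to treatment-emergent events.

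Elsewhere the protocol treats worsening as reportable:

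- Section 7 defines it as an adverse event: "Any worsening (i.e., any clinically significant adverse change in frequency and/or intensity) of a preexisting condition" counts if it is associated in time with the product.
- Section 6.2.1 sets the monitoring task: "The investigator or qualified designee will assess each subject to evaluate for potential new or worsening AEs".
- Section 7.4 says how it is recorded: "Any adverse event which changes CTCAE grade over the course of a given episode will have each change of grade recorded".
- Table 7 sets the dating rule: "Record the start and stop dates of the adverse event".

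No section says which start date applies when a condition present before dosing worsens on treatment.

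**The concern.** A treatment-emergent definition normally has two limbs: events that begin after the first dose, and events present before it that get worse after it. Section 8.5 has only the first. Sections 6.2.1, 7 and 7.4 collect the information for the second, but the analysis definition does not use it.

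Toxicity by CTCAE is a secondary endpoint (Section 2.3.2). If its tables are built on treatment-emergent events, a patient whose event was on the form before dosing and rose in grade afterwards is not counted for that event. The error runs in one direction, towards lower toxicity. The other defaults in Section 8.5 run the opposite way: an event with an unclear start is presumed treatment-emergent, and an event with no recorded relationship is placed in the strongest related category.

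**Working it through.** The plan states no figure on this point, so there is nothing to reproduce. The check is to apply the Section 8.5 rule to the kinds of record that the protocol can generate, then to size the effect of one misclassified patient.

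**Step 1. Can an adverse event with a pre-dose start be on the form?** Yes. Section 7 requires all adverse events to be reported from treatment allocation. Section 5.1 asks for treatment to begin on the day of allocation or close to it, so there can be a gap. Before allocation, Section 7 requires a report only if the event leads to exclusion or results from a protocol-specified intervention.

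**Step 2. What does the rule do with each record?** The cases are illustrative.

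| Case | How it is recorded | Start date used | Treatment-emergent under 8.5? |
|---|---|---|---|
| A | Baseline abnormality held as medical history; worsening on treatment entered as an adverse event | Date of worsening | Yes |
| B | Adverse event entered before the first dose; grade rises after it, logged as a grade change in the same episode (Section 7.4) | Pre-dose date | No |
| C | As B, but the worsening is entered as a new adverse event | Date of worsening | Yes |
| D | As B, with the start date incomplete but clearly before dosing | Pre-dose | No |

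Cases B and C are the same clinical course with opposite classifications. Section 7.4 supports B and the worsening clause in Section 7 supports C. In case D the missing-date rule does not help, because it exempts events whose dates show a pre-dose start.

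**Step 3. Does a No reach the toxicity result?** Only if the tables use treatment-emergent events. Section 8.5 defines the term and gives it an imputation rule, but never says where it is used.

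**Step 4. Size per patient.** With the 43 patients of Section 3.2:

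- one patient: 1/43 = 2.3 percentage points;
- four patients: 4/43 = 9.3 percentage points.

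The range of one to four is an assumption that shows scale; the documents give no number. Section 8.2.3 expects enrolment of up to 50. If all 50 were the safety denominator, one patient would be 1/50 = 2.0 points.

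**The case against.** The strongest reply is that Section 7 already handles worsening. It makes the worsening itself the adverse event, and Table 7 dates the adverse event, so the natural start date is on treatment and the Section 8.5 rule is met. Active conditions go into medical history (Section 6.1.3), as do abnormal examination findings (Section 6.2.2). Appendix 1 schedules adverse event review from Cycle 1, with no mark at screening. Pre-dose entries should therefore come mainly from the short interval between allocation and first dose. This largely stands, and it confines the problem to cases B and D. It does not remove it, because Section 7.4 provides for a single episode with changing grades and no section sets the start date.

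The second reply is that Section 8.5 summarises adverse events without restriction. That also stands: omission from the tables is conditional on a choice the plan does not state.

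A reader might infer two stronger conclusions, and the documents support neither.

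- **Worsening of baseline laboratory abnormalities is excluded as a class.** Section 3.3.1 admits AST and ALT up to 2.5 times the upper limit, creatinine up to 1.5 times and platelets down to 100,000/mcL. Sections 4.2.5 and 4.3.5 name hepatic, renal and platelet harms. But a permitted screening value is not shown to be an adverse event record; if it is held only as medical history it follows case A and is counted.
- **One misclassified patient could erase the hepatotoxicity signal.** Section 4.2.5 quotes 2% for Grade 3 to 5 hepatotoxicity, and 0.02 x 43 = 0.86 expected patients. That rate covers all patients on ipilimumab 3 mg/kg, whereas this regimen gives 1 mg/kg with pembrolizumab and aspirin. It is not a rate among patients with a pre-dose event on record, so it does not measure this bias.

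**Conclusion.** The definition in Section 8.5 is incomplete and does not match Section 7. An adverse event recorded before the first dose that rises in grade within the same episode fails it as written, and a table restricted to treatment-emergent events would then understate toxicity.

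The number of patients affected is unknown and probably small. A downward bias requires three things together: an adverse event on the form with a pre-dose start, the later grade increase logged under that same entry, and tables limited to treatment-emergent events. If either of the last two fails, the bias is zero. The documents fix neither, so the reported rate depends on data-entry practice and an unstated table convention.

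A reader might also infer a gap in live safety oversight. The documents do not support that: Appendix 3 has all Grade 3 to 5 events entered in the trial management system and reviewed monthly, regardless of attribution. The point concerns reported rates only. It is an analysis definition, not a rule of clinical management.

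**What to change.** In Section 8.5:

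1. Define a treatment-emergent adverse event as one that starts after the first dose, or that was present before the first dose and increases in CTCAE grade after it.
2. For events that qualify by worsening, take the date of the first post-dose grade increase as onset and the maximum post-dose grade as severity.
3. State that the toxicity tables use this set.

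Cases B, C and D above are then classified alike, whichever way the worsening was entered. Use CTCAE grade in the new clause, since Section 2.3.2 names it for the endpoint and Section 7.4 records it; Section 8.5 currently describes severity in four verbal categories.

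The cost is a few sentences and minor programming. No new data are needed, because Section 7.4 already collects each grade change. This assumes that each change can be dated; Section 7 has events recorded at each examination, so the visit date would serve if no other is captured.

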## Abstract

Title	Prostaglandin Inhibition and PD-1/CTLA4 blockade in melanoma
Patient population	Patients with stage III unresectable/ stage IV melanoma
Rationale for Study	Prostaglandin Inhibition may increase the efficacy of immunotherapy
Primary Objective	To evaluate the overall response rate (ORR) by week 12 in patients with stage III unresectable/stage IV melanoma.
Secondary Objectives	To determine the median progression free survival and the overall survival and toxicity profile of this combination.
Study Design	Prospective single arm Simon 2 stage Phase II trial
Number of patients	43
Duration of Follow up	Patients will be followed for 30 days after discontinuation of treatment or removal from study
Duration of study	The study is expected to complete accrual at 24 months.
Study Drugs	Aspirin Pembrolizumab Ipilimumab
Safety Assessments	CTCAE v. 4 will be used to assess toxicity.
Efficacy Assessments	RECIST version 1.1 will be used in this study for assessment of tumor response.
Unique Aspects of this Study	Combination trial with ipilimumab, pembrolizumab, and aspirin.

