#### 2.3.2 Secondary Endpoints

- Toxicity, according to CTCAE v. 4
- Profession Free Survival (PFS)
- Overall Survival (OS)

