**Table 7 Evaluating Adverse Events**

An investigator who is a qualified physician, will evaluate all adverse events as to:

V4.0 CTCAE Grading	Grade 1	Mild; asymptomatic or mild symptoms; clinical or diagnostic observations only; intervention not indicated.
	Grade 2	Moderate; minimal, local or noninvasive intervention indicated; limiting age-appropriate instrumental ADL.
	Grade 3	Severe or medically significant but not immediately life-threatening; hospitalization or prolongation or hospitalization indicated; disabling; limiting self-care ADL.
	Grade 4	Life threatening consequences; urgent intervention indicated.
	Grade 5	Death related to AE
Seriousness	A serious adverse event is any adverse event occurring at any dose or during any use of Merck product that:	
	† Results in death ; or	
	† Is life threatening ; or places the subject, in the view of the investigator, at immediate risk of death from the event as it occurred (Note: This does not include an adverse event that, had it occurred in a more severe form, might have caused death.); or	
	† Results in a persistent or significant disability/incapacity (substantial disruption of one's ability to conduct normal life functions); or	
	† Results in or prolongs an existing inpatient hospitalization (hospitalization is defined as an inpatient admission, regardless of length of stay, even if the hospitalization is a precautionary measure for continued observation. (Note: Hospitalization for an elective procedure to treat a pre-existing condition that has not worsened is not a serious adverse event. A pre-existing condition is a clinical condition that is diagnosed prior to the use of a Merck product and is documented in the patient's medical history.); or	
	† Is a congenital anomaly/birth defect (in offspring of subject taking the product regardless of time to diagnosis); or	
	Is a new cancer (that is not a condition of the study) (although not serious per ICH definition, is reportable to the Sponsor within 24 hours and to Merck within 2 working days to meet certain local requirements); or	

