#### 3. Review and Oversight Requirements

##### 3.1 Adverse Event Monitoring

All Grade 3-5 adverse events (AEs), whether or not considered to be expected or unexpected and whether or not considered to be associated with the use of the investigational agent(s) or study procedure, will be entered into OnCore®, UCSF's Clinical Trial Management System.

Adverse events are graded according to the Common Terminology Criteria for Adverse Events (CTCAE) as developed and revised by the Common Therapy Evaluation Program (CTEP) of the National Cancer Institute. Adverse events are further given an assignment of attribution or relationship to investigational agent or study procedure. Attribution categories are:

- **Definite** – The adverse event is clearly related to the investigational agent(s) or study procedure.
- **Probable** – The adverse event is likely related to the investigational agent(s) or study procedure.
- **Possible** – The adverse event may be related to the investigational agent(s) or study procedure.
- **Unrelated** – the adverse event is clearly not related to the investigational agent(s) or study procedure.

All Grade 3-5 adverse events entered into OnCore® will be reviewed on a monthly basis at the Site Committee meetings. The Site Committee will review and discuss the selected toxicity, the toxicity grade, and attribution assignment.

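### Section 8.5 summarises adverse event severity on four levels that stop short of CTCAE Grade 5, so the planned maximum-severity table has no level for a fatal event

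*Combined protocol and SAP*

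**What the plan says.** Section 2.3.2 defines the safety endpoint as "Toxicity, according to CTCAE v. 4". The abstract agrees ("CTCAE v. 4 will be used to assess toxicity"), and so do the two sections on data collection. Section 6.2.1 states: "Adverse experiences will be graded and recorded throughout the study and during the follow-up period according to NCI CTCAE Version 4.0". Section 7.4 requires that a qualified physician "will evaluate all adverse events according to the NCI Common Terminology for Adverse Events (CTCAE), version 4.0", and that every change of grade within an episode be recorded. Table 7 sets out the five grades, with Grade 5 defined as "Death related to AE".

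Section 8.5 uses other words: "The severity of each AE will be classified as mild, moderate, severe, or potentially life threatening". The same section then sets the counting rule "For summaries of adverse events by maximum severity or maximum relation to study drug": a subject with several occurrences is counted once, at the worst level. It does not mention CTCAE, gives no rule for converting grades to the four labels, and plans no separate table of fatal events.

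**The concern.** The toxicity profile of the three-drug combination is a stated secondary objective (section 2.2), and the ipilimumab safety text in section 4.2.5 warns of fatal immune-mediated reactions. The table meant to summarise that objective stops one level below the top of the scale on which the endpoint is defined. An analyst who follows section 8.5 literally has two choices for a death due to an AE. The first is to count it as potentially life threatening, which hides the outcome. The second is to leave it unclassified, so that the patient appears at the level of some lesser event or not at all. The plan does not say which, so the presentation of the gravest safety outcome would be settled after the data are seen.

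**Working it through.** The plan gives no figure to reproduce here; the check is a comparison of two scales.

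**Step 1. Set the scales side by side.**

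| Table 7 (CTCAE v4.0) | Section 8.5 label |
|---|---|
| Grade 1, mild | Mild |
| Grade 2, moderate | Moderate |
| Grade 3, severe or medically significant | Severe |
| Grade 4, life threatening | Potentially life threatening |
| Grade 5, death | none |

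Table 7 has 5 levels and section 8.5 has 4. The first four correspond in order; the missing level is Grade 5.

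**Step 2. Ask whether another planned analysis supplies the missing level.**

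- Serious AE reporting (section 7.3.1 and Appendix 3, section 3.2) captures deaths, but as a reporting duty.
- Appendix 3, section 3.1 provides that "All Grade 3-5 adverse events entered into OnCore® will be reviewed on a monthly basis at the Site Committee meetings". This is oversight during the trial.
- Overall survival (section 8.4.2) counts death from any cause and so does not separate toxic deaths from deaths due to melanoma.

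None of these is a summary of AEs by maximum severity.

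**Step 3. Size of one event.** The design has 43 evaluable patients and section 8.2.3 allows up to 50 to be enrolled. No safety population is defined, so both denominators are shown: 1/43 = 2.3% and 1/50 = 2.0%.

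**Step 4. Effect on the Grade 3/4 comparison.** Section 1.2.2 cites Grade 3/4 rates of about 20% (pembrolizumab with ipilimumab 1 mg/kg) and 50% (ipilimumab with nivolumab). By Step 1, severe plus potentially life threatening gives the Grade 3/4 count. If fatal events are merged into the top label, that sum becomes Grade 3-5, and it differs from Grade 3/4 only by the patients with a fatal AE, at 2.0 to 2.3 percentage points each.

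**Step 5. Could the missing row be needed? (Illustration only.)** Section 4.2.5 cites fatal reactions at ipilimumab 3 mg/kg: 4 from enterocolitis, 0.2% hepatic (taken as 1 patient), 1 dermatologic and 1 neurologic. Assuming no overlap and 511 as the common denominator, 7/511 = 1.4%. The chance of at least one fatal event is 1 − (1 − p)^n:

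- p = 7/511: 44.7% for n = 43 and 49.8% for n = 50.
- p from an assumed 0.2% to 2.0%: about 8% to 58% for n = 43, and about 10% to 64% for n = 50.

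These rates come from a different ipilimumab dose and regimen. They show only that the row cannot be presumed empty; the finding does not rest on them.

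**The case against.** The best defence is that section 8.5 is loosely worded CTCAE. Its four words follow the Table 7 descriptors, and the endpoint, the abstract, section 6.2.1 and section 7.4 all name CTCAE v4, so a sensible analyst would add Grade 5 unprompted. The grades are collected, death is a seriousness criterion assessed apart from grade, related deaths go to the monitoring committee leadership within one business day, and section 8.5 itself refers to subject data listings.

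Most of that stands, and it limits the point. A reader might infer three stronger things that the documents do not support:

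- **That the safety table could not be compared with the cited Grade 3/4 rates.** It largely could, because the labels line up with Grades 1 to 4 (Steps 1 and 4).
- **That toxic deaths would be lost.** They would not: they are recorded, reported as serious events and reviewed monthly.
- **That only treatment-related deaths are affected.** The severity scale applies to every AE, so the gap covers fatal AEs of any attribution.

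What the defence does not do is make section 8.5 right. It is the sole analysis text for this endpoint, it states a scale explicitly, and that scale contradicts the endpoint definition. Relying on the analyst to depart from the written rule is not prespecification.

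**Conclusion.** The point holds in a narrow form. Section 8.5 omits the fatal level of the scale that defines the secondary safety endpoint, so the planned maximum-severity summary would merge a fatal AE with Grade 4 or leave it unclassified. Each such event represents 2.0% to 2.3% of patients, depending on whether 50 or 43 is the denominator. The conclusion rests only on the text of section 8.5, section 2.3.2 and Table 7, and on reading section 8.5 as written. It affects no efficacy estimate, error rate or stopping decision, and it does not touch data capture or safety oversight. It is a stated rule that conflicts with the trial's own endpoint, and should be corrected before the safety tables are produced.

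**What to change.** In section 8.5:

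- Replace the four-label sentence with a statement that severity is the CTCAE v4.0 grade, 1 to 5, as recorded under section 7.4.
- Tabulate maximum grade per subject with Grade 5 as its own level, once for all AEs and once for treatment-related AEs, using the definition of related that section 8.5 already gives.
- Add a listing of fatal AEs with their attribution.
- State the denominator for these tables, since 43 and 50 both appear in the plan.

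The cost is a wording amendment and one extra level in the table programs. The grades are already collected, so no new data, visits or patients are needed.
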